5.15.2 Patient Withdrawal

A patient (or patient's LAR) may choose to withdraw from the study at any time without penalty or loss of benefits. The patient should notify the investigator (or designee) of his/her desire to withdraw, and the investigator (or designee) should ask for and document the reason for withdrawal. The investigator may also choose to withdraw a patient from the study at any time if he/she considers it to be in the patient's best interest. The reason for withdrawal should be recorded. Any data collected on the patient up to the point of withdrawal may be used in the study.

If complete wound closure has not been confirmed at the time of withdrawal from the study, then the investigator should attempt to determine the status of the wound at the time of the patient's withdrawal to the best of the patient's ability (i.e., healed, not healed, seeking additional treatment, not seeking additional treatment) and to complete as many of the patient-reported outcomes questionnaires as the patient is able and willing to complete.

5.15.3 Patient Lost to Follow-Up

The investigator should encourage patients to return for all required follow-up visits. A patient will be considered lost to follow-up after three documented phone call attempts or emails plus a certified letter that is sent to the patient's last known address in which no response is received. A patient should not be automatically exited from the study after a missed visit(s). Rather, the patient will remain in the study until he/she completes the final study visit required by the protocol, withdraws from the study, or is considered to be lost to follow-up.

5.15.4 Patient Death

If known, the cause of death should be documented.

5.15.5 Sponsor Discontinues Study

Premature termination of this clinical study may occur because of a regulatory authority decision, change in opinion of the IRB/EC, product safety concerns or at the discretion of Acera Surgical, Inc.

Acera Surgical, Inc. reserves the right to discontinue the study prior to inclusion of the intended number of patients but intends only to exercise this right for valid scientific or administrative reasons. After such a decision, the investigator must contact all participating patients within 30 days.

6. ADVERSE EVENTS (AE)

6.1 Principal Investigator Responsibilities

The investigator (or designee) should record and maintain all adverse events that occur over the course of the patient's participation in the study (randomization through study exit) during or outside of study visits. Adverse events that are reported to the sponsor will be assessed by an investigator. Adverse event assessments should include severity, seriousness, and relatedness to the product, study procedures and pre-existing conditions. See Section 6.4 for adverse events that are required to be reported to the Sponsor.

6.2 Adverse Event Definitions

Adverse Event:

Any untoward medical occurrence (sign, symptom, illness, abnormal clinically significant laboratory value, or other medical event) that occurs while the patient is enrolled in the study whether or not it is related to the study product or study procedures. A medical condition (pre-existing condition) that exists at study enrollment/randomization is not considered an AE unless the condition worsens after enrollment.

Serious Adverse Event:

A serious adverse event is any undesirable adverse event or untoward medical occurrence experienced by a patient during the study that:

- Results in death;
- Is life-threatening;
- Requires inpatient hospitalization or prolongation of an existing hospitalization;
- Results in persistent or significant disability/incapacity; or
- Requires intervention to prevent a permanent impairment of a bodily function or damage to a body structure.

Medical and scientific judgment should be exercised in determining whether an event is a serious adverse event. An important medical event may not be immediately life-threatening and/or result in death or hospitalization. However, if it is determined that the event may jeopardize the patient and may require intervention to prevent one of the other outcomes listed in the definition above, the adverse event should be reported as serious. Examples of such events are intensive treatment in an emergency room for a bronchospasm or convulsions that do not result in hospitalization.

This definition of an SAE is not intended to include hospitalization specifically to treat a condition that existed prior to the patient's enrollment in the study (e.g., pre-existing cardiovascular disease that is treated during the study) or prearranged elective surgery performed during this study period.

Adverse Device Effect:

Any adverse event that is caused by or associated with a study product.

Unanticipated Adverse Device Effect:

Any serious adverse effect on health or safety or any life-threatening problem or death caused by or associated with a study product, if that effect, problem or death was not previously identified in nature, severity or degree of incidence in the Protocol or Instructions for Use.

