6.3 Adverse Event Assessment

Adverse events that are required to be reported to the sponsor must be assessed by an investigator for severity, seriousness and relatedness to the product, study procedures and pre-existing conditions.

The following scale should be used for severity assessment:

ADVERSE EVENT SEVERITY	
Mild	AE is noticeable to the patient but does not interfere with routine activity and does not require medical treatment
Moderate	AE interferes with routine activity and/or requires medical treatment
Severe	AE results in loss of life, loss of limb, is life threatening, or results in permanent impairment of body structure or function

The following scale should be used for an assessment of relatedness to the study product, study procedure(s), and pre-existing conditions:

- Not Related
- Possibly Related
- Probably Related
- Definitely Related

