6.4 Adverse Event Reporting

The following adverse events are required to be promptly reported to the sponsor on the adverse event eCRF:

- Any serious adverse event whether or not it is related to a study product/procedure
- Any adverse event that in the opinion of the investigator is definitely related, probably related, or possibly related to a study product and/or study procedure
- The following adverse events whether or not they are related to a study product/procedure:
 - Infection of wound and/or area surrounding wound
 - Complete or partial amputation of lower extremity
 - Allergic reaction to a study product
 - Excessive redness, pain, swelling or blistering of wound

Serious adverse product effects should be reported to the sponsor as soon as possible. Pre-existing conditions or adverse events that occur prior to randomization are not required to be reported.

The investigator (or designee) is also required to report AEs to the IRB/EC if the AEs are required to be reported per the IRB/EC reporting requirements.

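### The SAE exclusion for pre-existing conditions has no exception for worsening, so some unplanned admissions can be classed as non-serious and, if judged unrelated, need not reach the sponsor

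*Combined protocol and SAP*

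**What the plan says.** The passages that bear on this are in the safety sections of the protocol.

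- **AE definition (6.2).** A condition present at enrollment "is not considered an AE unless the condition worsens after enrollment".
- **SAE definition (6.2).** One of five criteria is that the event "Requires inpatient hospitalization or prolongation of an existing hospitalization". The closing paragraph says the definition is "not intended to include hospitalization specifically to treat a condition that existed prior to" enrollment. The items that follow are "pre-existing cardiovascular disease that is treated during the study) or prearranged elective surgery performed during this study period".
- **Reporting to the sponsor (6.4).** The AE eCRF is required for "Any serious adverse event whether or not it is related to a study product/procedure", for any AE judged at least possibly related to product or procedure, and for four named types of event whatever their relatedness. The section adds: "Pre-existing conditions or adverse events that occur prior to randomization are not required to be reported".
- **Site records (6.1).** The investigator must keep a record of every AE from randomization to study exit.
- **Analysis (9.5.7.1 to 9.5.7.3).** Treatment-emergent AEs include events that get worse once randomized treatment has begun. SAEs and four AEs of interest are summarized separately.

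**The concern.** Two definitions in one section treat the same clinical event differently. A chronic disease that deteriorates after enrollment is an AE, but the admission it causes is taken out of the hospitalization criterion simply because the disease was already there.

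The population makes this more than a drafting nicety. Sections 4.1.1 and 4.2.1 require every DFU patient to have diabetes and every VLU patient to have venous disease, and every study ulcer to be more than 28 days old. Everyone in the trial therefore has conditions to which the exclusion can apply. For a product applied to a chronic wound, unplanned admissions for the limb, the wound or the underlying disease are among the safety events a reader would most want counted. What is at stake is the completeness of the SAE table and, for some events, whether the sponsor hears of them at all.

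**Working it through.** No figure in the plan is in dispute, so no arithmetic applies. The check sets the rules side by side and follows an event through them.

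**1. Is the exclusion confined to planned admissions?** No. Prearranged elective surgery is a separate item, joined by an or, and the example for the first item is existing cardiovascular disease treated during the study. If the first item covered only planned care, listing prearranged surgery separately would add little.

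**2. Is it confined to conditions that have not worsened?** Not in its wording. The qualifier appears in the AE definition (6.2) and the treatment-emergent definition (9.5.7.1). It is absent from the SAE exclusion and from the sentence on pre-existing conditions in 6.4.

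**3. Follow one event.** Take a DFU patient with an unplanned admission for decompensated diabetes that resolves without lasting harm and was not life-threatening.

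- AE? Yes: a pre-existing condition worsened (6.2).
- SAE by hospitalization? No, on the literal wording: the admission treats a condition that predates enrollment.
- SAE by another criterion? Only if the event met one of the other four (death, threat to life, lasting disability, intervention to avert permanent impairment or damage) or was judged an important medical event.
- Severity grade? The middle grade, defined as "AE interferes with routine activity and/or requires medical treatment" (6.3). The top grade needs death, limb loss, threat to life or permanent impairment, so severity does not recover the event.
- Reportable to the sponsor? If not an SAE, only if judged at least possibly related or on the 6.4 list. Diabetic decompensation is not on that list.
- In the analysis? If judged unrelated, it has no required route to the AE eCRF. If the summaries are built from that form, the event can be absent from 9.5.7.1 as well as 9.5.7.2. It still stands in the site record (6.1).

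**4. Repeat for other events.**

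- *Worsened cardiovascular or limb vascular disease:* the same path, unless another seriousness criterion is met.
- *Wound infection, amputation, or marked local wound reaction (redness, pain, swelling, blistering):* reportable whatever the relatedness (6.4), then summarized under 9.5.7.1 and 9.5.7.3. The 6.4 list does not make these events serious, so an admission for one could still be classed as non-serious.
- *Deterioration of the ulcer with none of those features:* the same path as diabetes, unless judged at least possibly related.

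**5. Conditions for each loss.** Missing the SAE table requires the literal reading and no other route to seriousness. Missing sponsor reporting requires, in addition, a judgement of unrelated and absence from the 6.4 list.

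**The case against.** The strongest reply is that the exclusion is narrower than it looks and other rules catch most of what matters. Several parts of that stand.

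- The exclusion names hospitalization only. The other four criteria remain, and 6.2 directs that an event that may jeopardize the patient and need intervention be reported as serious. Severe limb ischaemia or diabetic decompensation could qualify that way. Amputation grades as severe under 6.3 and plausibly meets the disability criterion.
- Active infection and undrained abscess are exclusion criteria in both arms, and osteomyelitis or exposed bone in the DFU arm (4.1.2, 4.2.2). A later infection or osteomyelitis can fairly be called a new condition, outside the exclusion.
- The 6.4 list and the possibly-related rule would bring in many admissions arising from the treated wound, and 6.3 requires every AE reported to the sponsor to be assessed for seriousness.
- An investigator could read the exclusion in the light of the AE definition above it and take the cardiovascular example to mean routine care of stable disease.

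These points narrow the gap without closing it. An ordinary admission for worsened chronic disease need meet no other criterion, the important-medical-event clause depends on judgement, and the benign reading has to be supplied by the site because the text does not state it. Sites that read it differently would report differently.

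A reader might infer that all admissions for the ulcer, diabetes or vascular disease fall outside the SAE table, or that wound infections and amputations appear only as AEs of interest. Neither follows: the other routes to seriousness remain, and reported events also enter the all-AE summaries.

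**Conclusion.** The point holds as a gap in a safety definition. The SAE exclusion in 6.2 conflicts with the AE definition beside it and with the treatment-emergent definition in 9.5.7.1. On its literal reading, an unplanned admission for a worsened pre-existing condition that meets no other seriousness criterion is not an SAE. The exposure is clearest for diabetes and for cardiovascular or limb vascular disease, and extends only in some cases to the ulcer.

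The size is unknown. A reader might multiply an assumed admission rate by the planned 110 DFU and 60 VLU patients, but the documents give no admission rate and no basis for the share that would escape every other route. That all patients carry a pre-existing condition shows how widely the wording applies, not how many events would be lost.

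Nor do the documents show that under-reporting would differ between groups. Section 5.8 lists AE assessment after randomization among the tasks of staff who obtain the assignment, so a difference is conceivable, but nothing indicates its direction or extent.

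The AE and SAE outputs are descriptive. The primary endpoint, sample size and interim rules are unaffected.

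**What to change.** Amend the closing paragraph of the SAE definition in 6.2 so that it excludes only hospitalizations planned before enrollment, or elective procedures, for a pre-existing condition that has not worsened. State there that an unplanned admission for worsening of any pre-existing condition, including the study ulcer, meets the hospitalization criterion. Add the same qualifier to the sentence on pre-existing conditions in 6.4, so that the AE, SAE, reporting and treatment-emergent rules agree.

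If patients have already been randomized, the records required by 6.1 allow earlier admissions to be reclassified under the amended rule, so that one definition applies throughout.

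The cost is a short amendment with the IRB approval that 11.2 requires, site retraining, somewhat more SAE forms and a higher reported SAE rate in all groups. Any reclassification adds a review of site records.

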6.3 Adverse Event Assessment

Adverse events that are required to be reported to the sponsor must be assessed by an investigator for severity, seriousness and relatedness to the product, study procedures and pre-existing conditions.

The following scale should be used for severity assessment:

ADVERSE EVENT SEVERITY	
Mild	AE is noticeable to the patient but does not interfere with routine activity and does not require medical treatment
Moderate	AE interferes with routine activity and/or requires medical treatment
Severe	AE results in loss of life, loss of limb, is life threatening, or results in permanent impairment of body structure or function

The following scale should be used for an assessment of relatedness to the study product, study procedure(s), and pre-existing conditions:

- Not Related
- Possibly Related
- Probably Related
- Definitely Related

6.4 Adverse Event Reporting

The following adverse events are required to be promptly reported to the sponsor on the adverse event eCRF:

- Any serious adverse event whether or not it is related to a study product/procedure
- Any adverse event that in the opinion of the investigator is definitely related, probably related, or possibly related to a study product and/or study procedure
- The following adverse events whether or not they are related to a study product/procedure:
 - Infection of wound and/or area surrounding wound
 - Complete or partial amputation of lower extremity
 - Allergic reaction to a study product
 - Excessive redness, pain, swelling or blistering of wound

Serious adverse product effects should be reported to the sponsor as soon as possible. Pre-existing conditions or adverse events that occur prior to randomization are not required to be reported.

The investigator (or designee) is also required to report AEs to the IRB/EC if the AEs are required to be reported per the IRB/EC reporting requirements.

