9.5.7 Adverse Events

9.5.7.1 All Adverse Events

Summaries of incidence rates of individual AEs overall will be prepared. Only treatment emergent AEs will be analyzed (a treatment emergent adverse event is one that started or worsened in severity at or after start of randomized treatment). Because a patient may experience more than one AE, summaries will provide both the number of patients experiencing at least one event and the number of events within a reporting period. Percentages provided will be the percent of patients experiencing one or more adverse events. In addition, incidence of AEs will be presented by severity (mild, moderate, severe) and by relationship to investigational product or procedure. Patients experiencing an event more than once will be counted under the maximum severity/relationship experienced.

A listing of all adverse events will include the patient number, AE number, days since index procedure, the AE name, the severity of AE, whether or not the AE is classified as serious (SAE), the relationship of the AE to the study product or procedure, the action taken, and the outcome.

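### The All Adverse Events tables in 9.5.7.1 are assured to hold only the events that 6.4 makes reportable, so they cannot support an overall adverse event rate or an overall group comparison (minor)

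*Combined protocol and SAP*

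**What the plan says.** **Site record.** Section 6.1: "The investigator (or designee) should record and maintain all adverse events that occur over the course of the patient's participation in the study". The same section then refers to 6.4 for the events that must go to the sponsor.

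**eCRF.** Section 6.4: "The following adverse events are required to be promptly reported to the sponsor on the adverse event eCRF". Its list has three classes:
- every serious event, irrespective of attribution;
- events admitted on the investigator's judgement: "Any adverse event that in the opinion of the investigator is definitely related, probably related, or possibly related to a study product and/or study procedure";
- four named types that enter irrespective of attribution: wound-area infection, lower-extremity amputation, allergy to a study product, and excessive local wound reactions such as redness or blistering.

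**Grading.** Section 6.3 requires severity, seriousness and relatedness for events that must be reported to the sponsor. Section 6.1 says that events reported to the sponsor are assessed by an investigator.

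**Analysis.** Section 9.5.7.1, headed All Adverse Events, states: "Summaries of incidence rates of individual AEs overall will be prepared". It adds breakdowns by severity and relationship and a listing of all events. Its only stated restriction is to treatment-emergent events. Section 9.5 has all results shown by treatment group and study arm. AE incidence is a tertiary outcome (Sections 1 and 3), and 9.5.6 plans no tests of tertiary endpoints.

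**The concern.** The events that must be entered are a narrower set than the events the tables claim to describe. Section 6.2 defines an AE without regard to relatedness, and the heading of 9.5.7.1 promises all of them. For a non-serious event outside the four named types, mandatory entry depends on the investigator's opinion about relatedness, and the people handling AEs after randomization know the assignment.

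Two things are at stake. The percentage of patients with any AE may be too low, in a document whose stated purpose (2.2) includes informing payers. Two percentages printed side by side also invite comparison, tested or not, and that comparison would partly reflect how relatedness was attributed. The severity and relationship breakdowns have the same weakness.

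**Working it through.** The documents give no AE rate, safety sample size or safety power, so there is no plan figure to reproduce. The check is a comparison of sections, followed by an illustration on assumed values.

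**Step 1: what reaches the database.**

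| Type of event | Site record (6.1) | eCRF entry required (6.4) | Grading required (6.3) | Expected in 9.5.7.1 |
|---|---|---|---|---|
| Serious | yes | yes | yes | yes |
| Four named types, related or not | yes | yes | yes | yes |
| Other non-serious, judged at least possibly related | yes | yes | yes | yes |
| Other non-serious, judged not related | yes | not stated | not stated | yes |

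The mismatch is in the last row. No section requires those events to be entered, and none says they are left out of the tables. In the relationship table, the not-related category for non-serious events is assured only for the four named types.

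**Step 2: who applies the filter.** Section 5.9 has blinded evaluators leave before randomization. In 5.8, AE assessment after randomization is listed with obtaining the assignment and applying the product, apart from the evaluator's tasks. Section 5.12 has un-blinded personnel collect AEs at virtual visits. It also has the investigator decide whether a DFU patient on standard of care (SOC) may forgo reapplication, which requires knowing the assignment. The relatedness opinion is therefore formed with knowledge of the group.

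**Step 3: what the filter can do.** Let *p* be the true proportion of patients with an event subject to the filter (non-serious and not among the four types), equal in both groups. Let *c* be the share judged at least possibly related. If sites enter only mandatory events, the displayed rate is *p* × *c*, and the false difference is *p* × (*c*_matrix − *c*_control). All values of *p* and *c* below are assumptions. With *p* = 0.30:

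| *c* matrix | *c* control | Displayed rates | Difference |
|---|---|---|---|
| 1 (all entered) | 1 | 30% vs 30% | 0 |
| 0.3 | 0.3 | 9% vs 9% | 0 |
| 0.4 | 0.2 | 12% vs 6% | +6 points |
| 0.5 | 0.1 | 15% vs 3% | +12 points |
| 0.2 | 0.4 | 6% vs 12% | −6 points |

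At 55 patients per DFU group (110 / 2), the +6-point case is about 6.6 against 3.3 patients. With shares of 0.5 and 0.1, the difference is 0.10 × 0.4 = 4 points at *p* = 0.10 and 0.50 × 0.4 = 20 points at *p* = 0.50.

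**Step 4: effect on the any-event percentage.** Section 9.5.7.1 counts patients with at least one event, so a patient already counted for a serious or named event cannot widen the gap. If 30% in each group are already counted, independently of the filtered events (an assumption), the +12 points shrink to (1 − 0.30) × 12 = 8.4 points.

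Under-counting thus needs only that sites enter no more than 6.4 requires. A false group difference also needs unequal attribution.

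**The case against.** A reader might infer that the tables will contain only reportable events, that unrelated events never reach the database, and that the group comparison is biased. The documents do not support this, for four reasons.

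- Section 6.4 says what must be reported promptly; it does not bar other entries. Sections 5.1, 5.2 and 5.10 have AEs assessed at every treatment visit, and 9.5.7.1 promises a full listing. A site could enter everything, and under 6.1 whatever it reported would be assessed.
- The filter does not govern all non-serious events. The named wound, limb and allergy events, which are among the most relevant to a wound product, enter whether or not they are judged related.
- Bias between groups needs unequal attribution, which is not shown. Dressing-based SOC may make product attribution less likely in the DFU control group. But 6.4 also admits events possibly related to a study procedure, and SOC patients have debridement and weekly applications against biweekly matrix, so the direction could reverse. In the VLU arm both groups receive an applied skin substitute on the same biweekly schedule, so the argument from dressing care does not carry over.
- The serious-event (9.5.7.2) and event-of-interest (9.5.7.3) summaries are already planned, and no test of AE incidence is.

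All four stand, and they limit the point to what the plan assures. They do not remove it: no section gives a route for the remaining events, and permission to enter them is not a requirement. Uneven practice between sites would itself make the overall rate hard to interpret.

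**Conclusion.** The point holds as a mismatch between collection and analysis. As written, the plan assures the 9.5.7.1 tables and listing only for events reportable under 6.4, so it does not assure the overall AE rate that their heading implies. Overall incidence would be understated if sites enter only mandatory events. The by-group display may be distorted in either direction if attribution differs by group.

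Neither size nor direction can be derived from the documents. The range of −6 to +12 points at *p* = 0.30 comes from assumed attribution shares, includes zero when they are equal, and shows the mechanism without estimating it.

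The point is minor. It concerns a descriptive, untested tertiary outcome and leaves the primary endpoint, sample size and error rate untouched. The serious-event and event-of-interest summaries do not pass through the relatedness filter, although deciding that a reaction is allergic or a wound sign excessive is still a judgement by people who know the assignment.

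**What to change.** Reconcile Sections 6.1, 6.3, 6.4 and 9.5.7.1 by one of two routes.

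1. **Relabel.** Retitle the 9.5.7.1 tables and listing *Adverse events reportable to the sponsor under 6.4*. State that unlisted, non-serious events judged unrelated need not have been entered. Claim no overall AE rate and no overall group comparison from these tables. Rest the by-group safety comparison on the summaries in 9.5.7.2 and 9.5.7.3. Align the allergy item: 6.4 collects allergic reactions to a study product, whereas 9.5.7.3 tabulates allergic reactions without that qualifier. The cost is wording and table titles, with no extra data collection; the price is that no overall AE rate can be claimed.

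2. **Collect.** Require eCRF entry and grading of severity, seriousness and relatedness for every AE that sites already record under 6.1, and keep the 6.4 list as the rule for prompt reporting. This supports the tables as now titled, at the cost of more data entry and investigator assessment at each site.
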